***No Day 15 visit starting from Cycle 4**

- [1] Subjects may continue treatment beyond 3 cycles (9 weeks) of SCB01A treatment per investigator discretion if they are experiencing clinical benefit, until the study is terminated. Refer to Table 2 for the schedule of assessments for additional treatment cycles.
- [2] EOT visit should be conducted 14 or 21 days (±2 days) after last infusion, depending on last infusion was given on Day 8 or Day 1, respectively. Early withdrawal visit should be conducted after the subject received the last dose of study treatment. A toxicity follow-up (can be done by phone contact) should be performed 28±3 days after the last dose of study treatment.
- [3] All AEs including SAEs must be reported from the time of start of study treatment and must continue to be followed for 28 days after last administration of study treatment.
- [4] ECG will be performed prior to study drug administration (pre-infusion, 0 hr), and then at the end of the infusion (24 hr) on Days 1 and 8 of additional treatment cycles beyond Cycle 3 (time window at each sample collected: ±30 min).

- [5] Tumor assessments will be assessed by using computerized tomography (CT) or MRI scans according to RECIST v1.1 at baseline, end of the first 3 cycles, and every three cycles thereafter until progression of disease (i.e. at or within 4 days prior to Day 1 of Cycle 4, 7, 10 and so on). For subjects who meet objective response criteria after the first 3 cycles of study treatment, confirmative radiological tumor assessments will be performed at least 4 weeks later.
- [6] Hematology: Hemoglobin, Hematocrit, MCV, MCHC, MCH, RBC count, WBC count, WBC Differential, Absolute neutrophil count and Platelet count
Coagulation: PT, and INR
Chemistry: Total Bilirubin, Alkaline Phosphatase, ALT, AST, Gamma-glutamyl transferase (GGT), Albumin, Total Protein, Creatinine, Urea (BUN), Uric acid, Total Creatinine Kinase (Ck) (if total Ck is above the ULN for the laboratory, Troponin-T or Troponin-I will be determined), Sodium, Potassium, Calcium, Chloride, Glucose, Triglycerides (TG) and Amylase.
The following lab panel will only be assessed at Screening Visit and EOT/Early Termination Visit: Creatinine Clearance, Total Cholesterol, High-Density Lipoprotein (HDL), Low-Density Lipoprotein (LDL), and Lipase.
- [7] Urinalysis: pH, Appearance, Color, Specific gravity, Viscosity, Turbidity, Ketones, Bilirubin, Blood, Glucose, Protein, Nitrites, Urobilinogen, Leukocyte esterase, Microscopic exam includes bacteria, cast, crystals, epithelial cells, RBC, and WBC.
- [8] i.v. infusion for 24-hour of SCB01A on Days 1 and 8 of each cycle in a 3-week cycle (time window: 24 hours \pm 10 min).
- [9] To be performed for all subjects at baseline and then during the trial only if grade 2 or above neurological symptoms experienced by the subject after receiving treatment with SCB01A. Refer [Section 5.9](#) for further details.
- [10] To be performed when necessary at the subject's request or per Investigator decision.

Table 3: Study Schedule, Follow-Up Phase

Study Visit [1]	FU1	FU2	FU3	FU4	FU5	FUx [2]	Unscheduled
Study Days*	85 (±3)	106 (±3)	127 (±3)	190 (±7)	253 (±7)	NA	NA
Study Weeks*	12	15	18	27	36	NA	NA
Activities							
Survival Status [3]	X	X	X	X	X	X	X
Cancer Therapy [4]	X	X	X	X	X	X	X

*This reflects the time points for subjects who didn't receive additional treatment cycles beyond Cycle 3. For subjects who undergo additional treatment cycles the follow-up visits will be conducted after discontinuation of treatment at every 3 weeks during the first 9 weeks, thereafter every 9 weeks until the end of the study.

- [1] Follow-up visits will be performed after the subject completes EOT visit or early withdrawal visit. Follow-up visits will be scheduled every 3 weeks for 9 weeks, thereafter every 9 weeks until the end of the study. These visits can be conducted by phone.
- [2] Additional follow-up visits every 9 weeks until the end of the study.
- [3] Follow-up for survival status will be performed via telephone call if the site is unable to confirm via chart review or clinical visit.
- [4] Cancer therapies evaluated at the Follow-Up visit or phone call include anti-cancer medications, cancer-related radiotherapy, and cancer-related surgery/procedures since last contact.

1. Introduction

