
 • ORR is defined as the percentage of subjects who have achieved confirmed CR and PR during treatment phase, according to RECIST v1.1. Not-confirmed CR or PR, or withdraw for DLT are counted as non-responder. • PFS is defined as the time from the start of treatment up to the date of first progression based on RECIST v1.1 or the date of death, whichever comes first. • OS is defined as the time from the start of treatment up to the time that the subject is still alive. • Best overall tumor response defined as the best response from start of treatment through all treatment phase or until disease progression/recurrence. 
Survival data will be collected throughout the active treatment phase and during the 27 weeks follow-up period. Survival follow-up after subject discontinuation of treatment will be conducted every 3 weeks during the first 9 weeks, thereafter every 9 weeks until the end of the study to assess for survival. Survival rate will only be assessed in subjects with measurable disease at baseline.
 
Dose Limiting Toxicity (DLT):
 
All toxicities will be classified according to the National Cancer Institute (NCI) Common Terminology Criteria for AEs (CTCAE) version 4.03. DLT will be defined as the occurrence of any of the following criteria unless there is definitive alternative evidence that administration of SCB01A did not cause the specific toxicity:
 
 • Grade 4 neutropenia exceeding 5 days' duration; • Grade 4 thrombocytopenia; • Grade 4 anemia; • Grade 3 or greater neutropenia with complications (e.g., fever, infection etc.); • Grade 3 or greater thrombocytopenia with complications (e.g., bleeding); • Grade 3 or greater non-hematological AEs including Grade 3 unmanageable nausea and vomiting that persist for 3 or more days after drug administration. Grade 3 fatigue lasting for ≤ 1 week is not considered as a DLT; • Grade 3 or greater prolonged QTc interval; • Grade 3 or greater neurotoxicity; • Delayed treatment exceeding 14 days duration due to drug-related toxicity; • Not able to recover from grade 2 neurotoxicity exceeding 3 weeks. 
Safety measurements:
 
The following safety assessments will be done during the study:
	

Name of Sponsor/Company: SynCore Biotechnology Co. Ltd.	
Name of Study Product: SCB01A	
Protocol Number: SCB01A-22	Indication: Recurrent or metastatic squamous cell carcinoma of head and neck

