Study Drug Administration [11]		X		X		X	X		X	X				
Nerve Conduction Velocity [12]	X													

[1] Subjects may continue treatment beyond 3 cycles (9 weeks) of SCB01A treatment per investigator discretion if they are experiencing clinical benefit, until the study is terminated. Refer to Table 2 for the schedule of assessments for additional treatment cycles.

[2] EOT visit should be conducted 14 or 21 days (±2 days) after last infusion, depending on last infusion was given on Day 8 or Day 1, respectively. Early withdrawal visit should be conducted after the subject received the last dose of study treatment. A toxicity follow-up (can be done by phone contact) should be performed 28±3 days after the last dose of study treatment.

- [3] All AEs including SAEs must be reported from the time of start of study treatment and must continue to be followed for 28 days after last administration of study treatment.
- [4] ECG will be performed prior to study drug administration (pre-infusion), and then at 10 and 24 hours after the start of infusion on Days 1 and 8 of Cycles 1, 2 and 3 and at pre-infusion and 24 hours after the start of infusion on Days 1 and 8 of Cycles beyond Cycle 3 (time window at each sample collected: ± 30 min).
- [5] Tumor assessments should be performed at baseline and at the end of Cycle 3 (at C4D1/EOT visit). Any additional assessment can be arranged when clinically indicated.
- [6] Hematology: Hemoglobin, Hematocrit, MCV, MCHC, MCH, RBC count, WBC count, WBC Differential, Absolute neutrophil count and Platelet count
Coagulation: PT, and INR
Chemistry: Total Bilirubin, Alkaline Phosphatase, ALT, AST, Gamma-glutamyl transferase (GGT), Albumin, Total Protein, Creatinine, Urea (BUN), Uric acid, Total Creatinine Kinase (Ck) (if total Ck is above the ULN for the laboratory, Troponin-T or Troponin-I will be determined), Sodium, Potassium, Calcium, Chloride, Glucose, Triglycerides (TG) and Amylase.
The following lab panel will only be assessed at Screening Visit and EOT/Early Termination Visit: Creatinine Clearance, Total Cholesterol, High-Density Lipoprotein (HDL), Low-Density Lipoprotein (LDL) and Lipase.
The following lab panel will only be assessed at Screening Visit: Hepatitis B/C
- [7] Urinalysis: pH, Appearance, Color, Specific gravity, Viscosity, Turbidity, Ketones, Bilirubin, Blood, Glucose, Protein, Nitrites, Urobilinogen, Leukocyte esterases, Microscopic exam includes bacteria, cast, crystals, epithelial cells, RBC, and WBC.

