1.2. Rationale for the Study

The research data available to date indicate that SCB01A is a promising anti-cancer agent with vascular disrupting activity that has potential for treatment of various malignancies, particularly for patients with drug resistance to existing therapies. The drug has been trialed in human subjects in dose-escalation phase I study, and maximum tolerated dose (MTD) is 24 mg/m² (each cycle consists of one intravenous [i.v.] administration of SCB01A via a central line every 3 weeks). In the phase I study, partial response (PR) (shrinkage of tumor size to 50%) was observed in cycle 9 (3 mg/m²) of one subject with right buccal squamous cell carcinoma and disease stabilization lasted for 14 cycles. Summary from current clinical findings note a total of 19/33 (57.6%) subjects had stable disease (SD) for at least 2 cycles. Extended disease stabilizations were especially observed for 23 cycles in one subject with cholangiocarcinoma (4 mg/m²) and 15 cycles in one subject with rectal cancer (3 mg/m²) respectively, suggested that the most prominent SD subjects remain in low dose (less than 6.5 mg/m²).

Pre-clinical study of SCB01A showed that the concentrations at which tubulin inhibition occurred were around 80 nM for 24-hour exposure or 200 nM for 6-hour exposure. However, pharmacokinetic (PK) results of both phase I study and an ongoing phase II study showed that the average elimination half-life (t_{1/2}) of a 3-hours i.v. infusion of SCB01A is approximately 2.5 hours and almost no SCB01A can be detected after 10 hours, indicating most subjects were treated in short API exposure time and may have been insufficient to achieve efficacy. Furthermore, clinical experiences demonstrated that extended infusion duration may reduce susceptible chemotherapy induced adverse reaction especially peripheral neuropathy (JCO 1999, 17(11): 3403-11). Summary from both efficacy and safety evidences suggesting that to extend the cumulative exposure duration of SCB01A beyond effective concentration in blood may be benefit to patient's best interest.

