3.3. End of Treatment (EOT) Evaluation/Early Withdrawal

EOT visit should be conducted 14 or 21 days (± 2 days) after last infusion, depending on last infusion was given on Day 8 or Day 1, respectively. Early withdrawal visit should be conducted after the subject receives the last dose of study treatment.

The following assessments will be performed at the EOT/early withdrawal visit:

- Physical examination
- Vital signs
- ECOG performance status
- AEs
- Concomitant medication
- 12-lead ECG
- Tumor assessment (radiological imaging)
- Laboratory tests (hematology, clinical chemistry and coagulation)
- Urinalysis

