8.2. Determination of Sample Size

Assumption of sample size calculation:

- Study design: Simon's optimal two stage design¹
- Type I error (one-sided): 5%
- Power: 80%
- Response probability of null hypothesis (P0): 0.05
- Response probability of SCB01A (P1): 0.20

According to these hypotheses, up to 37 subjects need to be recruited into the study (including 10 evaluable subjects in the Stage I and 19 evaluable subjects in Stage II, with the additional 8 subjects to account for replacement of subjects those who withdraw, i.e. dropout rate is 20%). At least 4 subjects are required to achieve CR or PR after treatment with SCB01A for the study to meet its primary objective. The trial will be discontinued if no objective response is observed after the Stage I tumor assessment review.

Stopping rule: The study will be stopped early for futility if less than 1/10 evaluable subjects showed ORR in Stage I; with no further investigation of the drug is less than 4/29 evaluable subjects achieve ORR by the end of Stage II.

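### A responder who stops drug in Cycle 3 or 4 has no scheduled confirmation scan, and the ORR definitions disagree on whether a confirmation after stopping counts

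*Protocol*

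**What the plan says.** **Confirmation.** The synopsis (Criteria for Evaluation) and Table 2, footnote 5, state that for subjects meeting response criteria after the first 3 cycles "confirmative radiological tumor assessments will be performed at least 4 weeks later". The sentence does not require the subject to be still on drug. Table 1 footnote 5 and sections 3.2.11, 3.3 and 6.1 do not mention this scan, and no visit column is assigned to it.

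**Scan times.** Table 1, footnote 5: "Tumor assessments should be performed at baseline and at the end of Cycle 3 (at C4D1/EOT visit". Table 2, footnote 5, allows the scan up to 4 days before Day 1 of Cycles 4, 7, 10 and so on. Section 3.3 puts imaging at the end-of-treatment (EOT) visit and says "EOT visit should be conducted 14 or 21 days (± 2 days) after last infusion", for a last infusion on Day 8 or Day 1 respectively. Table 3 (follow-up) lists only survival status and cancer therapy, and those visits may be by phone. Unscheduled imaging is permitted.

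**Scoring.** Synopsis: "Not-confirmed CR or PR, or withdraw for DLT are counted as non-responder". SAP 9.8 has the same rule. Both restrict confirmed responses to the treatment phase. Protocol 6.1 instead speaks of a confirmed response at some time point after first treatment.

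**The concern.** The primary endpoint depends on a second scan at least 28 days after the first. If drug is stopped soon after the response scan, the visit tables end imaging before day 28. A site that then does the required scan off treatment may still not secure the response, because two of the three definitions tie confirmation to the treatment phase.

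Such a subject also stays in the analysis. Someone who completed 3 cycles and has a post-baseline scan meets the per-protocol definition (8.3), is not replaced under 3.1, and counts as a non-responder among the 29, unless the Medical Monitor excludes the subject for a deviation or adverse event.

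The protocol's own rules can produce this case. Section 4.9 ends treatment when a related Grade 3 or 4 event recurs after resuming, while uncomplicated Grade 3 neutropenia is not in the DLT list in 6.2. A responder can therefore stop with neither progression nor a DLT. With decision limits of 1/10 and 4/29, a single reclassified subject can matter.

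**Working it through.** **1. Reproduce the design.** Inputs from 8.2: Simon's "optimal two stage design", one-sided 5%, power 80%, "Response probability of null hypothesis (P0): 0.05", P1 = 0.20, stop at 0/10, success at 4/29 or more.

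P(success | p) = Σ (x = 1 to 10) C(10,x) p^x (1−p)^(10−x) × P(Bin(19,p) ≥ 4−x)

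- p = 0.05: 0.0468
- p = 0.20: 0.8011
- Recruitment: 29/0.80 = 36.25, rounded up to 37

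A grid search also returns this as the optimal design for these inputs. The plan's figures are correct.

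**2. Scan timing.** C4D1 is day 64 and C4D8 is day 71 (Table 2). EOT = Day 1 infusion + 21, or Day 8 infusion + 14. The response scan is nominally on days 60 to 64.

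| Last infusion | EOT day | Days after a day-64 scan |
|---|---|---|
| C3D1 (day 43) or C3D8 (day 50) | 64 | 0 (the same scan) |
| C4D1 (day 64) or C4D8 (day 71) | 85 | 21 (25 after a day-60 scan) |
| C5D1 (day 85) or C5D8 (day 92) | 106 | 42 |

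**3. Windows for a Cycle 4 stop.** Let a = C4D1 shift (±1), s = days the scan precedes C4D1 (0 to 4), b = C4D8 shift (±1), e = EOT shift (±2).

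- Last dose C4D8: gap = 21 + b + e − a + s. The range is 21 − 1 − 2 − 1 + 0 = 17 to 21 + 1 + 2 + 1 + 4 = 29. There are 3 × 5 × 3 × 5 = 225 combinations. A gap of 28 or more needs the four shifts to total 7 or 8, which happens in 4 + 1 = 5 of them.
- Last dose C4D1: a cancels, so gap = 21 + e + s, range 19 to 27. It never reaches 28.

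From a Cycle 5 stop onward, the EOT scan is late enough.

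**4. Responses first seen later.** C7D1 is day 127 and C10D1 is day 190, 63 days apart, which satisfies the 4-week minimum. A stop in Cycle 8 gives EOT on day 169, 42 days after day 127. The 21-day gap recurs only for a stop in Cycle 7 (EOT day 148).

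**5. The definitions applied to one subject.** PR at the end of Cycle 3, drug stopped in Cycle 4 without progression or DLT, PR confirmed off treatment at 28 days or later.

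- Synopsis and SAP 9.8: a non-responder if the treatment phase ends when drug stops or at EOT. The term is not defined.
- Section 6.1: a responder.

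**6. Sensitivity (assumption).** The documents do not give the share f of true responders left unconfirmed. Replace p by p(1−f) in the formula above; the Stage I stop probability is (1−p(1−f))^10.

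| f | Response rate | Power | Stage I stop | Alpha, with 0.05(1−f) |
|---|---|---|---|---|
| 0 | 0.20 | 80.1% | 10.7% | 4.7% |
| 5% | 0.19 | 76.8% | 12.2% | 4.0% |
| 10% | 0.18 | 73.0% | 13.7% | 3.4% |
| 20% | 0.16 | 64% | 17.5% | 2.3% |
| 30% | 0.14 | 53.4% | 22.1% | 1.5% |

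**The case against.** The strongest reply is that the scan is already mandatory. Footnote 5 says it will be done, without an on-treatment condition, and a minimum interval needs no fixed visit when unscheduled imaging is allowed. Section 3.8.2 also encourages subjects who stop drug to stay in the study so that progression can be followed. This stands. A reader might infer from the visit tables that early stoppers can have no confirmation scan, or that true responses are routinely scored as failures; the documents do not support either. They leave open where the scan sits and whether it counts.

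The affected group is also small. Progression before 4 weeks means there was no confirmed response. DLT withdrawals are non-responders by explicit rule. Subjects with fewer than 3 cycles for reasons other than drug toxicity are replaced. Those who withdraw consent entirely cannot be scanned under any wording. All of this stands, but a subject who completes 3 cycles and stops without progression or DLT remains exposed.

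A reader might also infer that late responses are lost, because "partial response (PR) (shrinkage of tumor size to 50%) was observed in cycle 9" in phase I. That does not follow. The footnote is ambiguous for a response first seen at Cycle 7 or later, but the next routine scan at 63 days can confirm it. In the phase I subject, disease control lasted 14 cycles, and under this schedule scans would fall at Cycles 10 and 13.

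Finally, 6.1 does not exclude off-treatment confirmation. But 6.1 carries an open drafting note about aligning it with the synopsis, and the SAP follows the synopsis, so the wider definition cannot be relied on.

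**Conclusion.** The point holds as a mismatch between schedule and endpoint definition. The required confirmation scan has no visit. After a last infusion in Cycle 3 or 4, the last scheduled scan falls 0 days or nominally 21 to 25 days after the response scan, and reaches 28 days only at window extremes when C4D8 is the last dose. The ORR definitions then disagree on a response confirmed after drug is stopped without progression.

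The bias is conservative: it can cost power or add to Stage I futility stops, but it does not raise alpha. Its size is unknown. The fall from 80% to 73% rests on an assumed 10% loss and should not be read as an estimate. If the planned 20% already means confirmed response under this schedule, nothing is lost against plan. It is still worth correcting, because the narrower rule can turn a confirmed responder into a non-responder against a threshold of 4 in 29.

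**What to change.** **ORR definition** (synopsis, 6.1, SAP 9.8): use one text. A CR or PR first seen at any assessment and confirmed by a scan at least 28 days later counts as confirmed, even if study drug was stopped without progression, provided neither progression nor new anti-cancer therapy came before that scan. This is an analysis rule only and does not delay therapy of the clinician's choice.

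**Schedule** (Table 1 and Table 2 footnote 5, 3.3, 6.1): state that the confirmation scan already required applies to these subjects.

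- Response first seen at the EOT scan: confirmation is a separate scan at least 28 days later. Moving the EOT scan cannot help here, since it is itself the response scan.
- Response seen earlier and EOT due before 28 days: the EOT imaging is timed at or after 28 days.

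**Cost:** wording, plus, in a few subjects, EOT imaging nominally 3 to 7 days later (28 − 25 to 28 − 21) or one already intended scan done off treatment.

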1.1. Background

Vascular disrupting agents (VDAs) are designed to disrupt the already abnormal vasculature that supports tumors by targeting their already dysmorphic endothelial cells. VDAs induce rapid and selective shutdown of the tumor blood supply resulting in tumor death while leaving the blood supply in normal tissues relatively intact^{2,3}. The largest group of VDAs is the tubulin-binding combretastatins. Combretastatin A4 phosphate (CA4P) is a small organic molecule found in the bark of the African bush willow tree (*Combretum caffrum*)². Endothelial cells have been shown to be particularly sensitive to the effects of CA4P compared with various other cell types and several preclinical studies have demonstrated selective *in vitro* activity of CA4P against proliferating endothelial cells².

SCB01A is a novel heterocyclic combretastatin A-4 (CA-4) analogue that binds to the colchicines-binding site of the β -subunit of tubulin thereby inhibiting polymerization and effectively preventing mitosis in a manner similar to that seen with other “spindle poisons”, e.g., vincristine, vinblastine and vinorelbine, which are in use as cancer chemotherapeutic agents. Because SCB01A has VDAs property, SynCore plans to develop SCB01A as a treatment for a variety of oncologic indications such as non-small cell lung cancer, breast cancer, head and neck cancer, acute lymphoblastic leukemia, nephroblastoma and testicular cancer.

Compounds that interfere with the cell cycle by interfering with normal biology of tubulin are prominent anti-cancer agents because they can inhibit the proliferation of tumor cell lines derived from various organs. Tubulin-containing structures are important for diverse cellular functions, including chromosome segregation during cell division, intracellular transport, development, and maintenance of cell shape, cell motility, and possibly distribution of molecules on cell membranes. The drugs that interact with tubulin are heterogeneous in chemical structure. However, a common characteristic of these agents is that while binding to tubulin, they cause its precipitation and sequestration to interrupt many important biologic functions that depend on the microtubular class of subcellular organelles. One class of well-characterized and clinically used antimitotic drugs is those of natural origin, including the taxanes (paclitaxel, docetaxel), vinca alkaloids (vincristine, vinblastine, vinorelbine), and podophyllotoxins. These agents either inhibit the polymerization of tubulin (vinca alkaloids) or prevent the disassembly of microtubules (taxanes).

SCB01A has been studied extensively since 2005 to evaluate its pharmacokinetic (PK) profile, metabolism, *in vitro* genotoxicity, and acute and sub-acute toxicity. SCB01A binds to colchicine binding sites of tubulin much more strongly than colchicines, and as with other antimicrotubule inhibitors, it arrests the cells on the G2/M phase in a time- and concentration-dependent manner, subsequently leading to cell apoptosis. Additional studies indicate that the effect of SCB01A on cell-cycle arrest is associated with an increase in cyclin B1 levels and a mobility shift of Cdc2 and Cdc25C. The changes in Cdc2 and Cdc25C coincide with the appearance of phosphoepitopes

recognized by a marker of mitosis, MPM-2. Furthermore, phosphorylated forms of Bcl-2, perturbed membrane mitochondrial potential, and activation of the caspase 3 cascade may be involved in SCB01A-induced apoptosis.

